6.4 Final Visit, Visit 03, Day 85+7 Days Post-dose, Phone Visit

- The participant will be asked if they or their partner became pregnant. If the participant became pregnant, the Pregnancy Report and Follow-Up forms will be completed. If the participant's partner became pregnant, details about the pregnancy should be reported to the sponsor to document the outcome of the pregnancy. All SAEs will be recorded on the appropriate DCF/DMID SAE Report Form.

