6.5 Missing Data

All attempts will be made to collect all data per protocol. As missing data are expected to be minimal, no imputation or other missing data methods will be performed for missing values other than for partial or missing dates where complete dates are required to flag data as treatment emergent or concomitant with treatment. Partial or missing start and end dates for AEs and concomitant medications will be imputed such that if the missing part of the date causes ambiguity in the temporal relationship to treatment, it will be assumed to be treatment emergent or concomitant. Specifically, dates will be imputed as follows:

Partial and missing start dates

- Dates with missing day only will be imputed as the first of the month unless the month and year are the same as the month and year of the study medication administration date, in which case missing day will be imputed as the day the participant received study medication unless the end date is on or before the date of study medication administration in which case it will be imputed as the first of the month the end date was reported, or the month prior if the end date is the first of the month.
- Dates with both day and month missing will be imputed as 01JAN unless the year is the same as the year of the study medication administration, in which case the missing day and month will be imputed

as the dose day and month the participant received study medication unless the end date is on or before the date of study medication administration in which case it will be imputed as 01JAN of the year the end date was reported, or 01DEC of the year prior if the end date is the first of the year.

- Completely missing dates will be imputed as the date of study medication administration unless the end date is on or before the date of study medication administration, in which case the missing date will be imputed as 01JAN of the same year as the end date was reported, or 01DEC of the year prior if the end date is the first of the year.

Partial and missing end dates

- Dates with missing day only will be imputed as the last of the month.
- Dates with both day and month missing will be imputed as 31DEC unless the year is the same as the year of the study medication administration, in which case the missing day and month will be imputed as the day and month of the participant's last study visit.
- Completely missing dates will be imputed as the date of the participant's last study visit.

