9.1.2 Prior and Concomitant Medications

Summaries of medications that were started prior to dosing and continuing at the time of dosing or initiated after dosing will be presented by WHO Drug at the Anatomical Therapeutic Chemical (ATC) Levels 2 and 3 and renal impairment group ([Table 78](#)). Individual participant listings will be presented for all concomitant medications ([Listing 15](#)).

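### SAP 6.5: a year-only end date in the dosing year can be imputed about nine months before dosing when the last study visit falls in the next calendar year

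*SAP*

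**What the plan says.** SAP 6.5 (Missing Data) states the aim first: where the missing part of a date leaves its relation to treatment unclear, "it will be assumed to be treatment emergent or concomitant". Specific rules follow.

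- **Year-only end date:** the default is 31DEC of the reported year. The exception is a reported year equal to the dosing year, "in which case the missing day and month will be imputed as the day and month of the participant's last study visit". The rule supplies a day and a month, not a year.
- **Completely missing end date:** "Completely missing dates will be imputed as the date of the participant's last study visit". Here the year of the visit is used.
- **Limits:** no end date is imputed for a record that is ongoing or of missing status, unless a death date is available. The only limit on an imputed end date is a cap at the date of death. There is no floor at dosing or at the record's own start.
- **Start dates:** each start-date rule looks at the end date. For a year-only start, the dosing day and month are used "unless the end date is on or before the date of study medication administration in which case it will be imputed as 01JAN" in the end year. For a completely missing start: "Completely missing dates will be imputed as the date of study medication administration unless the end date is on or before the date of" dosing.

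SAP 6.5 also says that imputed dates are used to derive treatment-emergence status.

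The last planned contact is Protocol 6.4: "Final Visit, Visit 03, Day 85+7 Days Post-dose, Phone Visit". SAP 9.1.2 summarises "medications that were started prior to dosing and continuing at the time of dosing or initiated after dosing". SAP 9.3 defines a treatment-emergent AE (TEAE) by onset or worsening on or after the dosing day, and leaves AEs that began before treatment out of the summary tables.

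**The concern.** Taking the day and month from one calendar year and the year from another is harmless only while the two years agree. Follow-up runs for about three months, so they differ for anyone dosed late in the year who completes it. The rule then returns a date long before dosing for a record that may have been active at or after dosing. That is the reverse of the aim stated at the top of the section. At stake are the classification of some medications as concomitant, the internal consistency of some AE dates and, under one reading of the imputation order, whether some AEs count as treatment-emergent.

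**Working it through.** The documents give no figure for this point, so the check applies the rule literally to the calendar.

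**Inputs.** Dosing is on Day 1 and the last visit on Day 85 to Day 92 (Protocol 6.4 and Appendix A). The last visit is therefore dosing + k days, with k = 84 to 91. The reported end year is the dosing year.

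**When the year changes.** The last visit falls in the next year if fewer than k days of the dosing year remain after dosing.
- k = 84: from 9 October to 31 December there are 22 + 30 + 31 = 83 days, so 9 October is the first affected date. 84 dosing dates are affected; 84/365 = 23.0%.
- k = 91: from 2 October to 31 December there are 29 + 30 + 31 = 90 days, so 2 October is the first. 91 dosing dates are affected; 91/365 = 24.9%.

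**How far before dosing.** The imputed date is the last-visit date moved back one year, so the gap is 365 (or 366) − k.
- k = 84: 281 or 282 days.
- k = 91: 274 or 275 days.

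Running through every dosing date in 2023 and 2024 gave the same cut-offs and gaps. Reading the visit as dosing + 85 or + 92 days moves the cut-off to 8 or 1 October and the gap to 280-281 or 273-274 days.

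**Example.** Dosed 15NOV2023; last visit 15NOV2023 + 84 days = 07FEB2024; end date reported as 2023. Imputed: 07FEB2023, which is 281 days before dosing.

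**Can that date be right?** Medications are reported back to 30 days before consent at the earliest (Protocol 7.1.1). Consent is given at most 28 days before dosing, so the earliest reportable use is about 30 + 28 = 58 days before dosing. AEs are collected from dosing onward (Protocol 8.1). An end date 274 or more days before dosing lies outside both windows.

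**Effect by type of record.**
1. *Medication started before dosing and taken at dosing.* With the imputed stop date it no longer meets the criterion in SAP 9.1.2.
2. *AE with a complete post-dose start.* It remains a TEAE, because status rests on onset, but its end precedes its start.
3. *AE with a partial or missing start.* It moves to before dosing only if the end date is imputed first and that value is then used in the start-date rule. The SAP does not give the order.

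**Participants possibly exposed.** With even enrolment over the year (an assumption), 12 × 0.230 to 0.249 = 2.8 to 3.0 participants in Part A, and 36 × 0.230 to 0.249 = 8.3 to 9.0 if Part B is run. These are people dosed in the window, not affected records.

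**The case against.** A reader might infer that everyone dosed from October receives a wrong end date. The documents do not support that. The end date must lack both day and month, its year must be the dosing year, the record must not be ongoing or of missing status, and the last visit must fall in the next year. Someone who terminates early within the dosing year is not affected.

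A reader might also infer that post-dose AEs drop out of the TEAE tables. That does not follow either. It needs an incomplete start date as well, and an imputation order the SAP does not give. Some of the start-date wording points to the end date as reported. A year-only end date has no reported month, so the rule for a start date missing only its day cannot be applied to it as written.

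Such records should be rare. Non-serious AEs are collected for about 11 days, participants are in hospital to 48 hours, AE start and stop dates are to be recorded, and missing items are queried. A drug still in use is recorded as ongoing. SAP 6.5 expects little missing data, shows original dates in listings and has odd values investigated. The medication table shell is titled as covering prior as well as concurrent medications, so a misdated drug might still be counted there.

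All of this stands and limits the reach. It does not rescue the rule. The general aim might lead a programmer to override the result, but the specific rules are given as its implementation and contain no override.

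**Conclusion.** The rule is wrong as written; the severity is minor. For a year-only, non-ongoing end date in the dosing year, with a last visit in the next year, it gives an end date about nine months (274 to 282 days) before dosing, against the section's own aim. With follow-up completed on schedule, this covers dosing from 2 October (Day 92) or 9 October (Day 85) to 31 December.

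The medication effect follows directly from the criterion in SAP 9.1.2. For an AE with a complete start, the effect is an end date before onset, with no change of TEAE status. Reclassifying an AE with an incomplete start as pre-treatment is possible but conditional on the unstated order. The number of affected records is not given, is probably small and could be zero. The primary PK results do not depend on these dates, and safety is descriptive. The figures rest on the literal text, on Day 1 being the dosing day and, for the participant counts only, on even enrolment.

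**What to change.** Replace the year-only end-date rule in SAP 6.5 with: 'A year-only end date is set to the earlier of 31DEC of the reported year and the full date (day, month and year) of the participant's last study visit, but never to a date before the reported start date.'

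When the reported year is the dosing year, both candidate dates are on or after dosing, so the result cannot precede it. The run over all dosing dates found 0 of 365 and 0 of 366 before dosing. In the example the imputed date becomes 31DEC2023.

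Also state that a start date is moved to before dosing only when the reported, non-imputed part of the end date itself shows that the record ended on or before dosing. A blanket ban on using imputed end dates for this would go too far: where the reported month or year already places the end before dosing, it would put the start after the end.

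The cost is two sentences in the SAP and a small change to the derivation code. No new data are needed.

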3 STUDY DESIGN, OBJECTIVES, AND ENDPOINTS OR OUTCOME MEASURES

3.1 Study Design Description

This is a Phase 1, open-label, single-dose, sequential group study to evaluate the PK and safety profile of pretomanid in participants with renal impairment (excluding those with ESRD needing dialysis) compared to matched participants with normal renal function.

The study will be conducted following a reduced PK study design in Part A, see [Table 1](#) and [Figure 1](#). Part A will enroll participants from Group 1A (i.e., 6 healthy matched controls) and Group 2 (i.e., 6 participants with severe renal impairment and ESRD, not on dialysis).

A decision to proceed to Part B will be made after the PK of pretomanid and safety of participants enrolled in Part A have been reviewed. If Part A demonstrates at least a 50% increase in pretomanid AUC in Group 2 (severe renal impairment and ESRD, not on dialysis) relative to the exposures in Group 1A (matched participants with normal renal function), then the reduced PK study will extend to the full PK study to enroll participants into Part B (i.e., to investigate mild and moderate renal impairment) and all enrollment will be initiated concurrently in Part B groups (1B, 1C, 3, and 4). Otherwise, no further study is recommended.

Study Population

Part A

Group 1A: 6 healthy participants (matched controls) with normal renal function: MDRD (eGFR ≥ 90 mL/min). Participants will be matched by race, gender, age (± 10 years, but between 18 to 85 years of age) and body mass index (BMI) (18 to 40 kg/m²).

Group 2: 6 severe renal impairment participants: Stage 4, MDRD (eGFR 15-29 mL/min), and ESRD not on dialysis, Stage 5, MDRD (eGFR < 15 mL/min).

Part B

Groups 1B and 1C: 6 healthy participants (matched controls) each, for Groups 3 and 4, respectively: MDRD (eGFR ≥ 90 mL/min). Participants will be matched by race, gender, age (± 10 years, but between 18 to 85 years of age) and BMI (18 to 40 kg/m²).

Group 3: 6 mild renal impairment participants: Stage 2, MDRD (eGFR 60-89 mL/min).

Group 4: 6 moderate renal impairment participants: Stage 3, MDRD (eGFR 30-59 mL/min).

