10 STATISTICAL CONSIDERATIONS

10.1 Study Hypotheses

FDA guidance document suggests using a reduced PK design for drugs that are predominantly metabolized or secreted in the bile [38]. In a reduced PK study design, the trial compares PK in patients with normal renal function and to patients with severe renal impairment and patients with ESRD not yet on dialysis. If the reduced PK study shows at least a 50% increase in AUC in patients with severe renal impairment and patients with ESRD not yet on dialysis relative to the matched healthy controls, a “full” renal impairment study in patients with all intermediate levels of renal function impairment should be conducted [38]. Otherwise, no further study is recommended.

In the current study, Part A is considered the reduced PK study in which the geometric mean ratio of AUC (AUC_{last} and area under the plasma concentration-time curve from time zero to infinity [AUC_{∞}]) will be determined comparing Group 2 participants (Severe renal impairment and ESRD, not on dialysis) to matched Group 1A participants (healthy participants with normal GFR). The ratio of geometric mean AUCs and 90% confidence interval (CI) of the parent compound will be considered in determining whether to continue with a full renal impairment study (enrollment of subsequent cohorts in Part B). Interim PK data of the parent compound will be reviewed by some members of the study team from DMID and TB Alliance before decision is made to proceed to Part B. For further details, please refer to the PK Manual.

[figure not shown]
In Part B, the primary intent will be to estimate PK parameters of the parent compound and metabolites and model the relationship between measures of renal function and the PK parameters to determine whether dosage adjustment is required for patients with impaired renal function. Estimates and CIs will be utilized rather than formal hypothesis tests.

No formal hypothesis tests are planned for safety analyses, but safety data will be collected and analyzed.

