4.4.6 Blinding

Not Applicable; this is an open-label study.

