5 SAMPLE SIZE CONSIDERATIONS

A sample size of 6 per group is standard for renal impairment PK studies. Prior studies of pretomanid (PA-824) with similar dosing (200 to 250 mg) have estimated coefficients of variation (CV) of 16% to 33% for the AUC after a single dose in healthy adult participants. Assuming a 20% CV for the AUC of both groups, the probability of observing at least a 50% increase in the geometric mean ratio of AUCs given a true 100% increase is >99%. The probability of the lower bound of the 90% CI for the geometric mean ratio of AUCs being at least 1.5 in this scenario is approximately 70%.

The sample size per arm in Part B was chosen based on feasibility and appropriateness for a PK study in renal impaired participants to estimate group differences in PK parameters with adequate precision. Assuming an observed 2-fold difference between each renal impairment group and matched controls with no correlation between matched pairs and a coefficient of variation of 20%, a 90% CI for the fold difference between groups is (1.70, 2.35).

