6.3.2 Pharmacokinetic Analysis Population

The PK analysis population will consist of participants who received pretomanid and provided sufficient bioanalytical assessment results to calculate reliable estimates of the PK parameters. Any participants or data values excluded from PK analyses will be identified, along with their reason for exclusion, in the clinical study report.

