- If the status is missing or it is indicated as ongoing then the date will not be imputed unless a death date is available, in which case the missing date will be imputed as the death date.
 - If the imputed date is after the date of death, the date will be set equal to the date of death.

Original dates as reported will be displayed in listings and the imputed dates will be used for derivations only, such as study day and treatment-emergence status.

Any data point that appears to be erroneous or inexplicable based on clinical judgment will be investigated as a possible outlier and may be excluded from analysis.

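### SAP 6.5 lets unexplained values be dropped on clinical judgment, with no all-data result required before the Part A decision; this matters when the AUC ratio is near 1.5

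*SAP*

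**What the plan says.** The last sentence of SAP 6.5 (Missing Data), after the date-imputation rules, covers "Any data point that appears to be erroneous or inexplicable based on clinical judgment". Such a point "will be investigated as a possible outlier and may be excluded from analysis". The sentence gives no numeric criterion, decision-maker or timing, and it is not limited to safety data.

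The setting is as follows.
- **Blinding** (SAP 4.4.6): "Not Applicable; this is an open-label study".
- **Size** (SAP 5): "A sample size of 6 per group is standard for renal impairment PK studies".
- **Gate** (Protocol 3.1): "If Part A demonstrates at least a 50% increase in pretomanid AUC in Group 2" relative to Group 1A, the study extends to Part B. Otherwise no further study is recommended.
- **How the gate is read** (Protocol 10.1): "The ratio of geometric mean AUCs and 90% confidence interval (CI) of the parent compound will be considered in determining whether to continue". Some study team members from DMID and TB Alliance review the interim PK data.
- **Disclosure** (SAP 6.3.2, and likewise Protocol 10.5.1.2): "Any participants or data values excluded from PK analyses will be identified, along with their reason for exclusion, in the clinical study report".

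Other PK data rules already exist: handling of values below the quantitation limit (SAP 10), removal of samples with laboratory-reported errors (SAP 10.1) and acceptance criteria for the terminal slope (SAP 10.2.2.1).

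**The concern.** The sentence treats inexplicable as a separate ground from erroneous, so a valid but surprising value qualifies. Laboratory errors already have their own rule, and a participant who vomits within two hours of dosing is already excluded (Protocol 4.3). What the sentence mainly adds is discretion without a documented cause.

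High AUCs in Group 2 are the signal that Part A looks for. The protocol reports that less than 1% of the drug is excreted unchanged in urine (2.2.1), so a high AUC in renal impairment could easily look hard to explain. Nothing requires the exclusion to be settled before the ratio is known. The disclosure duty attaches to the study report and not to the Part A review. If a trimmed ratio falls below 1.5 and Part B is not opened, a later listing does not reverse that. The plasma and urine subset analyses (SAP 6.3.2.1 and 6.3.2.2) are optional and post hoc, and they deal with problems in the other matrix, not with outliers.

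**Working it through.** **Inputs.** Six per group and planning CV 20% ("Assuming a 20% CV for the AUC of both groups"); prior-study CV range 16% to 33% (SAP 5); threshold ratio of 1.5 (Protocol 3.1). AUC is taken as log-normal with equal CV in both groups and no correlation within matched pairs. The ratio is the simple ratio of geometric means.

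**Step 1: the plan's own figures.**
- Log-scale SD = √ln(1 + 0.20²) = 0.198. Standard error of the log ratio = 0.198 × √(2/6) = 0.1143.
- P(observed ratio ≥ 1.5 | true 2.0) = Φ(ln(2.0/1.5)/0.1143) = Φ(2.516) = 99.4%. The SAP says more than 99%.
- P(lower 90% bound ≥ 1.5) = 69.7% from a noncentral t with 5 df. The SAP says about 70%.

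Both figures are reproduced, so the model below is the plan's own.

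**Step 2: effect of losing one participant.** If one of six log-AUCs lies a distance d from its group mean, dropping it moves that mean by d/5, and the ratio by a factor exp(d/5).
- At d = 2 SD and CV 20%: exp(2 × 0.198/5) = 1.08. An observed 1.40 becomes 1.51, or 1.60 becomes 1.48.
- The same factor is 1.07 at CV 16% and 1.14 at CV 33%.

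**Step 3: worst case, always dropping the highest Group 2 AUC.** The maximum of six lies on average 1.267 SD above the mean. The average shift is therefore exp(−1.267 × 0.198/5) = 0.951, a fall of 4.9%. At CV 33% (SD 0.3215) the fall is 7.8%. Simulation of 400,000 trials per CV gives:

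| True ratio | CV | P(observed ≥ 1.5), all data | Highest Group 2 AUC always removed |
|---|---|---|---|
| 1.6 | 20% | 71% | 55% |
| 1.6 | 33% | 64% | about 47% |
| 2.0 | 20% | 99.4% | about 98% |

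**Step 4: a milder reading.** Suppose the maximum is removed only when it lies more than 2 SD above its group mean. This happens in 13% of trials, since 1 − 0.977⁶ = 0.13. At a true ratio of 1.6 the probability then falls from 71% to 69% at CV 20%, and from 64% to 61% at CV 33%. The trigger is an assumption, because the SAP gives none.

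**Step 5: how far from 1.5 this matters.** This is the probability, at CV 20%, that excluding some one of the 12 participants would put the point estimate on the other side of 1.5:

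| True ratio | 1.0 | 1.25 | 1.4 | 1.5 | 1.6 | 1.75 | 2.0 |
|---|---|---|---|---|---|---|---|
| Reversal possible | 0.1% | 13% | 34% | 40% | 35% | 18% | 2.5% |

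At a true ratio of 2.0 it is 0.5% at CV 16% and 14% at CV 33%.

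**Step 6: losing one concentration instead.** I took a one-compartment profile with CL/F 8 L/hr and V/F 175 L (Protocol 2.1.5.2), an assumed absorption rate of 0.5 per hour, the planned sampling times, and linear-up log-down AUC. Removing a value wrong by a factor of 2 changes that participant's AUC by at most about 15%. The ratio then moves by 1.149^(1/6) = 1.023, or about 2.3%.

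**The case against.** The strongest objections concern size and reach.

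- **The worst case is not the rule.** The sentence requires investigation and says only that a point may be excluded. Step 4 shows a loss of two to three percentage points under a milder trigger. This stands, and the 16-point drop at CV 20% is an upper illustration, not an expected effect.
- **One exclusion is not decisive in general.** A reader might infer that with six per group any exclusion settles Part B. Step 5 does not support that: reversal is rare at no effect and, at CV 20%, at the planning ratio. SAP 6.5 also speaks of a data point, and SAP 6.1 makes the reported concentration the PK unit of analysis. One lost concentration matters only if the ratio is within about 2% of 1.5.
- **Who excludes is not stated.** A reader might also infer that people who know the group will choose exclusions with the ratio in view. The documents do not say so. They only fail to prevent it.
- **There are safeguards.** The Part A review uses cumulative data for all enrolled participants (Protocol 10.4.1, SAP 6.6), and Listings 6 and 22 carry exclusion reasons. Neither requires a ratio on all values at that review.
- **The gate is not mechanical.** The 90% CI is considered too, DMID and TB Alliance decide jointly, and the PK Manual, which was not available, may add rules. The probabilities above therefore describe the observed ratio, not the chance that Part B opens.

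**Conclusion.** The concern holds in a limited form. SAP 6.5 permits a value to be excluded because it cannot be explained, without a criterion, without a time limit relative to the ratio, and without an all-data result at the Part A decision. The risk is material when the AUC ratio is near 1.5 and a whole participant's AUC is removed. At CV 20%, the true ratios where reversal is a real possibility run from about 1.25 to 1.75. At the planning case the worst-case loss is about 1.5 percentage points (99.4% to about 98%).

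The figures assume log-normal AUCs, equal CV, no pair correlation and a simple geometric mean ratio without the site term. The documents do not support a claim that exclusions would be biased in practice, or that one exclusion would usually change the outcome. The case for changing the text is that the gap is avoidable and cheap to close.

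**What to change.** Replace the last sentence of SAP 6.5 for PK data with a rule on these lines:

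1. A PK value is excluded only for a documented bioanalytical, dosing or sampling error. The decision and its reason are recorded before the group AUC ratio is computed.
2. The prespecified PK rules stay in force: reliable parameter estimates (SAP 6.3.2), values below the quantitation limit (SAP 10), laboratory-reported errors (SAP 10.1) and terminal-slope criteria (SAP 10.2.2.1). A participant who fails the slope criteria still has no acceptable AUC to infinity, even with no documented error.
3. All other values stay in the primary analysis and in the Part A ratio.
4. Any other value queried as an outlier is removed only in a sensitivity analysis. The ratio and its 90% CI are shown both ways at the Part A review.

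If the PK Manual already contains such a rule, the SAP should cite it. The cost is SAP wording and one extra table, with no change to sample size or procedures. The downside is that a genuine but unexplained extreme value stays in and widens the confidence interval.
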